6.3. Selection criteria

Table 4. Selection criteria

Inclusion	Exclusion	Elimination
University of Colima students linked to the central campus.	Motor limitations that may hinder the performance of physical exercise.	Musculoskeletal injuries during the study period.
Students aged between 18		Unforeseen Medical Events: Unexpected medical

and 25 years old.	Pregnancy or lactation.	situations that could influence study results, such as hospitalizations, serious illnesses, or surgeries.
Authorization to participate in the project with a signed informed consent.	High Vigorous Physical Activity Level according to the IPA-Q.	Non-Compliance with Follow-Up: Subjects failing to meet a minimum of 80% (19 out of 24 sessions) of the stipulated physical conditioning program time.
Suffer from at least one of the parameters of metabolic disorders or cardiovascular risk (Hyperglycemia, decreased DHL, elevated triglycerides, abdominal obesity or hypertension) following the clinical assessment (Considering the criteria established by the ADA and ATPIII).	To be currently under pharmacological treatment to manage altered metabolic levels.	Initiation of clinical treatment that may affect protocol results, such as medications that reduce alterations.
		Participants who voluntarily withdraw from the study.

Source: self-made.

7. Variable operationalisation.

Table 5. Dependent variables.

Dependent variables	Operational definition	Nature	Scale	Instrument
Glucose Alterations	Fasting plasmatic glucose concentration determination:	Quantitative Continuous Ratio	It is considered an alteration >110 mg/dl	Fasting serum glucose

Abdominal Circumference	Total abdominal perimeter Abdominal obesity based on abdominal circumference.	Quantitative Continuous Ratio	It is considered an alteration when: Males >90cm Females >85 cm	Circumferential measurement with ISAK tape measure
HDL (High-Density Lipoprotein)	Serum concentration of high-density lipoprotein in milligrams per deciliter (mg/dl)	Quantitative Continuous Ratio	It is considered an alteration when: Males < 40 mg/dl, Females < 50 mg/dl	Lipid profile test
Triglycerides	Serum concentration of triglycerides in milligrams per deciliter (mg/dl)	Quantitative Continuous Ratio	It is considered an alteration when: Males >150 mg/dl Females >150 mg/dl	Lipid profile test
Arterial Hypertension	Subject's systolic and diastolic blood pressure measured in mercury millimeters (mmHg)	Quantitative Continuous Ratio	It is considered an alteration when: Males > 130/85 mmHg Females > 130/85 mmHg	Sphygmomanometer
Physical Activity Level	Physical Activity performed by the subject 7 days before the survey	Qualitative Ordinal	PA: Low, Medium, High	IPA-Q (International Physical Activity Questionnaire)
Physical Fitness Test: Aerobic	Subject's cardiorespiratory capacity using an	Qualitative Ordinal	Very Poor Poor Average	Quee's College Step Test

Capacity	effort test.		Good Excellent Superior	
----------	--------------	--	-------------------------------	--

Source: self-made based on the reference (11,105).

Table 6. Independent variables

Variable	Operational definition	Nature	Scale	Instrument
Aerobic physical exercise	Individually adapted aerobic physical exercise program meeting the WHO 2021 criteria and the FITT Principles.	Quantitative Continuous Ration	57% - 76%	Prescription

Source: self-made.

Table 7. Intervinient variables

Variable	Operational definition	Nature	Scale	Instrument
Age	Chronological age in years	Quantitative Continuous	18 - 24 years	Survey
Sex	Genetically corresponding sex	Qualitative Dichotomous nominal	Male and Female	Survey

Source: self-made.

8. Location for carrying out the protocol

University of Colima's Sports Center (central campus).

9. Study Procedure

Once the project is approved by the Bioethics Committee from the Faculty of Medicine at the University of Colima (Annex 1) and the Ethics Committee from Colima's Regional Hospital (Annex 2), annexing a no-conflict of interest letter (Annex 3), letters of intent will be prepared and sent to the directors of the faculties within the central campus of the University of Colima (Annex 4). Their purpose is to inform them about the project's generalities, obtain permission to share it with the students and address any questions they may have

Those who agree will receive an informed consent form (Annex 5) for their respective signatures. They will be informed about the appropriate attire for the study (for women, this includes sports shoes, leggings, and a top or T-shirt, and for men, shorts and a T-shirt), the requirement to fast for a minimum of 8 hours on the data collection day, and the date (Saturdays), time (8:00 am to 12:00 pm) and place (Faculty of Medicine, University of Colima) of the initial tests (these tests will also be considered the baseline for people who are found to have a metabolic alteration).

On assessment day, the project team will execute the following tests: application of the IPA-Q questionnaire (*annexe 6*), abdominal circumference (*annexe 7*), blood pressure (*annexe 8*), blood collection by venipuncture for HDL, triglycerides and glycemia (*annexe 9*), and the Queen's College step test (3 minutes) to determine their cardiorespiratory capacity (*annexe 10*), (after completing all the tests, every participant will receive refreshments and will be asked if they are in good condition to conclude their assessments, if not, they will be monitored until their answer is affirmative).

Once all blood samples are collected, they will be taken to the laboratory at the Faculty of Chemical Sciences, University of Colima, for processing. Simultaneously, data from the other assessments will be synthesized. When the final results from all 5 tests are collected, a sample of 48 subjects will be selected for the protocol, considering the established inclusion criteria (*Table 2*). With this sample, simple randomization will be performed in a new meeting, using sealed envelopes (each containing a letter indicating group assignment that will not be seen by

participants). Participants will draw an envelope and mark it with their names, and they will hand the envelope to the designated person (principal investigator).

At the end of the meeting, the envelopes will be opened by the organizers in the absence of the participants to reveal whether they belong to the (A) control or (B) experimental group. This process ensures single-blind criteria, where participants do not know their group assignment.

[figure not shown]
After forming the (A) control and (B) experimental groups, they will be divided to provide them instructions for compliance with the exercise program while maintaining single-blind conditions. In the control group (A), the exercise prescription used by Habibzadeh in 2010 will be implemented: which involves walking for 30 minutes at an intensity of 57% to 76% of the maximum heart rate, three times per week (Monday, Wednesday, and Friday) for eight weeks (*annex 11*). They will always be accompanied by a previously trained physical education student (Monitoring the intensity range in which the subjects must be during the session, will be done through the effort perception scale (*Annex 12*), heart rate at 15 seconds multiplied by 4 or the H10 polar monitor) (83). On the other hand, the experimental group (B) will engage in an aerobic exercise program (jogging, aquatic activities, and stationary cycling) lasting 40 to 60 minutes, three times per week (Monday, Wednesday, and Friday) for eight weeks, always under the supervision of the principal investigator. Each participant in the experimental group will receive a structured exercise prescription tailored to their specific condition, considering the established aerobic training ranges (57% to 63% of maximum heart rate) (*annexe 11*). (Monitoring the intensity range in which the subjects must be during the session will be done through the effort perception scale (*Annex 12*), heart rate at 15 seconds multiplied by 4 or the H10 polar monitor).

By the end of the first four weeks, the second round of assessments and samples will be done, taking into consideration: Abdominal circumference (*annexe 7*), blood pressure (*annexe 8*), blood collection by venipuncture for HDL, triglycerides and glycemia (*annexe 9*), and the Queen's College step test will be performed (3 minutes) (*annexe 10*), (after completing all the tests, every participant will receive refreshments and will be asked if they are in good

condition to conclude their assessments, if not, they will be monitored until their answer is affirmative). Subsequently, after completing sample collection and assessments, the control group (A) will continue with the same dynamics as in the initial weeks. The experimental group (B) will maintain the same exercises (jogging, aquatic activities, and stationary cycling), but their intensity may be adjusted from 64% to 76% of the maximum heart rate if favourable results are obtained from the cardiorespiratory fitness test (*annexe 11*), since this shows the level of evolution of the subject after the initial intervention and thus, the FITT-VP principle in exercise prescription would be fulfilled.

At the end of the last 4 weeks of the aerobic physical exercise program, the same sampling will be concluded; Abdominal circumference (*annexe 7*), arterial pressure (*annexe 8*), blood collection by venipuncture for HDL, triglycerides and glycemia (*annexe 9*), and the Queen's College step test will be performed (3 minutes) (*annexe 10*) (after completing all the tests, every participant will receive refreshments and will be asked if they are in good condition to conclude their assessments, if not, they will be monitored until their answer is affirmative), finishing the proposed intervention protocol.

10. Study flowchart

11. Statistical analysis

The statistical analysis will be conducted using the Statistical Package for the Social Sciences (SPSS) Statistics 26 from Business Machine (IBM). Descriptive statistics will be carried out, including measures of central tendency for the variables of age, sex and IPA-Q. Normality tests will be applied such as Kolmogorov-Smirnov for samples > 50 , and Shapiro-Wilk for samples < 50 . For the levels of triglycerides, glucose, HDL (High-Density Lipoprotein), abdominal circumference, and cardiorespiratory fitness, paired-sample T-tests will be used if the data follow a normal distribution, but if they do not, the Wilcoxon signed-rank test will be employed. To compare the control and experimental groups, independent-sample t-tests will be used if the data is normally distributed, otherwise the Mann-Whitney U test will be used. Likewise, a multivariate analysis will be carried out to relate the influence of physical exercise

on metabolic alterations. A significance level of $p \leq 0.05$ will be considered statistically significant.

12. Ethical considerations

According to international and national principles for research involving human subjects, as outlined in the Declaration of Helsinki and the General Health Law in its Articles 100 and 101 of Chapter V, Research for Health, and in the General Health Regulation regarding Research to Promote Health, specifically in Article 17, Section I, it is determined that this research is classified as a minimal-risk study. This categorisation is based on its approach: a study involving controlled and voluntary exercise intervention and blood extraction through venipuncture. The blood extraction will not exceed a maximum frequency of twice a week or a maximum volume of 450 ml, limited to only three samples during the identification of the protocol sample, at the midpoint, and upon completion (106). Additionally, Article 15 of the regulation stipulates that random selection methods will be adopted for experimental designs involving human subjects with multiple groups. Impartial assignment of participants to each group will be ensured, taking necessary measures to prevent risks or harm to research subjects. Immediate attention will also be provided by the team implementing this protocol if any adverse effects caused by exercise are observed. These criteria have been incorporated into the research planning (106).

Following the guidelines established by the Declaration of Helsinki, the privacy and confidentiality of information provided by participants will be safeguarded. An informed consent form (Annex 1) has been prepared, detailing the exclusive use of data for research purposes. This consent will be subject to approval by the Ethics and Research Committee (107).

The questionnaires, tables, and formulas used are scientifically validated and publicly available, affirming the certainty of the process and its results. Considering the above, this research protocol will undergo evaluation and approval by the Honourable Bioethics Committee of the Faculty of Medicine at the University of Colima. Following approval by this

committee, it will be submitted to the Ethics Committee of the University Regional Hospital of Colima, which will issue an opinion for its implementation, with the support of the Federal Commission for Protection against Sanitary Risks (Cofepris).

13. Human resources, financing and feasibility

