6.2 Sample size

The sample size was calculated with a formula to compare two means:

$$n = \frac{K(\sigma_1^2 + \sigma_2^2)}{(\mu_1 - \mu_2)^2}$$

Figure 5. Applied formula to calculate the sample size.

Source: Taken from García in 2013(104).

The sample size was determined through a study that assessed the impact of physical training on metabolic alterations. The pre-intervention measurements were 131.31 ± 22.53 , and the post-intervention measurements were 116.90 ± 12.88 (65)

Error $\alpha = .05$

Error $\beta = 0.2$ (20%)

Power $1 - \beta = .8$ (80)

$K = 6.2$

$\sigma^2 = 22.53$

$\sigma^2 = 12.88$

$\mu_1 = 131.31$

$\mu_2 = 116.90$

$n = 20 \pm 20\%$.

$n = 24$ subjects per group

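### Participants can be eliminated for events after randomisation, and no all-randomised analysis set or missing-data method is defined, so the group comparison would naturally be read as covering compliant completers only

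*Combined protocol and SAP*

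**What the plan says.** Table 4 in section 6.3 has an Elimination column, separate from Exclusion, with five conditions: musculoskeletal injury during the study; unforeseen medical events, described as "situations that could influence study results, such as hospitalizations, serious illnesses, or surgeries"; low attendance, "Subjects failing to meet a minimum of 80% (19 out of 24 sessions) of the stipulated physical conditioning program time"; "Initiation of clinical treatment that may affect protocol results, such as medications that reduce alterations"; and voluntary withdrawal. Section 9 randomises the 48 selected students after baseline testing and before any session, so attendance failures, and any of the other events after that meeting, are post-randomisation.

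Section 11 gives the group comparison as "To compare the control and experimental groups, independent-sample t-tests will be used if the data is normally distributed", with Mann-Whitney otherwise, and adds "Likewise, a multivariate analysis will be carried out to relate the influence of physical exercise" on metabolic alterations, not specified further. It names no analysis population, no missing-data method and no rule for eliminated participants.

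Follow-up is scheduled without any attendance condition. Section 9 sets a round of tests after four weeks and another at the end ("At the end of the last 4 weeks of the aerobic physical exercise program, the same sampling will be concluded"). Section 12 describes blood sampling as "limited to only three samples during the identification of the protocol sample, at the midpoint, and upon completion". Section 6.2 raises a calculated 20 to 24 "subjects per group" by 20% and gives no reason for the 20%.

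**The concern.** If eliminated participants leave the analysis, the two groups compared are no longer the groups that were randomised. They are the students who attended enough, stayed uninjured and started no treatment. The estimate then describes that selected subset, and the difference between arms can reflect who was removed as well as what the programme did.

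Unequal removal is plausible here. The programmes differ by arm, and so do the supervisors: a trained student accompanies the walkers, while the principal investigator supervises the experimental group (section 9). The organisers know the allocation when they apply the medical-event and new-treatment conditions, both of which call for judgement. Section 3 itself expects poor adherence in this population.

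There is also a point that cannot be repaired later. If elimination ended assessment as well, a participant could lose both follow-up values, and no analysis could recover them.

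**Working it through.** **1. The plan's own figure.** Section 6.2 gives K = 6.2, 131.31 ± 22.53 and 116.90 ± 12.88. With the two spreads squared:

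n = 6.2 × (22.53² + 12.88²) / (131.31 − 116.90)² = 6.2 × 673.50 / 207.65 = 20.1, taken as 20; 20 × 1.2 = 24 per group. This reproduces.

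**2. The attendance cut.** 0.80 × 24 = 19.2 sessions, and 19/24 = 79.2%. Exactly 19 sessions satisfies the bracket but not 80%. The bracket allows 24 − 19 = 5 misses. At three sessions a week, the sixth miss can fall as early as session 6, the end of week 2, before the week-4 assessment.

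**3. Possible bias.** The documents give neither removal rates by arm nor a link between attendance and outcome, so both are assumed.
- Standard deviation, from the section 6.2 figures: √((22.53² + 12.88²)/2) = 18.35 mg/dL. Triglycerides are used only because section 6.2 is built on them.
- Model: 24 per arm, no true effect, the k lowest attenders removed, correlation r between attendance and improvement.
- Bias in SD = r × [h(k₁) − h(k₂)], where h(k) is the expected mean of the 24 − k highest of 24 standard normal values: h(0) = 0, h(2) = 0.157, h(3) = 0.223, h(5) = 0.348.
- Example, 5 v 2 at r = 0.5: 0.5 × (0.348 − 0.157) = 0.0955 SD; × 18.35 = 1.75 mg/dL, in favour of the arm that loses more.

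| Removed | Bias at r = 0 / 0.1 / 0.3 / 0.5 (mg/dL) | Two-sided rejection across these r, simulated |
|---|---|---|
| 5 v 5 | 0 / 0 / 0 / 0 | 5.0% to just under 6% |
| 5 v 3 | 0 / 0.23 / 0.69 / 1.14 | 5.0% to about 6.3% |
| 5 v 2 | 0 / 0.35 / 1.05 / 1.75 | 5.0% to about 6.8% |
| 5 v 0 (extreme) | 0 / 0.64 / 1.91 / 3.19 | 5.0% to about 9.0% |

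Rejection rates are from at least 100,000 runs per cell with a t-test at 0.05; repeat runs differ by up to about 0.2 points. Only attendance-based removal is modelled, not injury, medical events or new treatment.

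**4. Cost in power of keeping everyone.** Two-sided noncentral-t power with SD 18.35. The difference of 14.41 is only an illustration: it is a before-after change in one cited study, and the control arm here also exercises. K = 6.2 matches a one-sided 0.05 test, (1.645 + 0.842)² = 6.18, which is why the two-sided figure at 24 per arm falls below 80%.

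| Analysed per arm | Difference (mg/dL) | Power |
|---|---|---|
| 24, no dilution | 14.41 | 76% |
| 19 completers (5 dropped) | 14.41 | 65% |
| 24, with 20% non-adherers gaining nothing | 0.8 × 14.41 = 11.53 | 57% |
| 24, with 20% non-adherers gaining half | 0.9 × 14.41 = 12.97 | 67% |
| 24, with 10% non-adherers gaining nothing or half | 12.97 or 13.69 | 67% or 72% |

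**5. Laboratory numbers.** 48 × 3 = 144 of the 150 lipid and 150 glucose tests in Table 8, leaving 6 for students screened but not enrolled.

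**The case against.** The strongest reply is that the plan never says eliminated data are dropped. The assessments are scheduled for everyone, and elimination could mean only that the exercise stops. The confirmed defect would then be an undefined analysis set, not a per-protocol analysis. This stands in part. A reader might infer that the plan prescribes a completers-only analysis; it does not say so, and the section 10 flowchart could not be read. But nothing in the available text supports the narrower meaning. The column sits within the selection criteria, and two of its entries are justified by their effect on results. Even under the narrower meaning the analysis set stays open and could be chosen after the data are seen.

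A reader might also take the rise from 20 to 24 as evidence of planned removal, or as a basis for a lopsided loss such as 4 v 0. Neither follows. The increase is unexplained and fits an ordinary allowance for missing values under an all-randomised analysis. It also applies to each group, so it would suggest 4 v 4, which gives no bias if the mechanism is the same in both arms.

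The simulated bias is modest and rests on assumed correlations. That is right, and the case does not depend on it.

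The mismatch between 80% and 19 of 24 could be called rounding. It still leaves a participant with exactly 19 sessions unclassified.

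**Conclusion.** The concern holds in this form: elimination conditions operate after randomisation, and section 11 ties them to no all-randomised set and no missing-data method. Confidence in that gap is high. That the comparison would cover only compliant completers is the natural reading, but an inference, and is held with less confidence.

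The size and direction of any bias cannot be derived from the documents, and they do not show that it would favour the experimental arm. On the assumptions above, moderately unequal removal matters little to moderately, and only the extreme case brings the rejection rate to about 9%. Voluntary withdrawal is unavoidable and is not part of the fault.

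This should be settled before enrolment, because follow-up values that are never collected cannot be restored. The argument is one of validity: all-randomised power may be lower or higher than completers' power.

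**What to change.** - **Section 6.3:** state that meeting an elimination condition neither removes data nor ends the scheduled week-4 and week-8 assessments for participants who still consent. Whether they continue exercising is a separate clinical matter on which this point takes no position.
- **Section 11:** make the main between-group comparison all randomised participants in their assigned group, with a stated missing-data method, for example a mixed model on the baseline, week-4 and week-8 values. Say which set the multivariate analysis uses and how values after new treatment are handled.
- **Sensitivity and reporting:** keep the attendance-defined set as a labelled sensitivity analysis, and report eliminations and reasons by arm.
- **Attendance wording:** reconcile 80% with 19 of 24, so that it is clear whether exactly 19 sessions qualifies for that set. Session durations also conflict between section 9 and Annexe 11 (Tables 11 and 12); that is a separate inconsistency to reconcile.

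The cost is wording, follow-up of non-adherers at visits already scheduled, and possible dilution of the effect. The laboratory budget needs checking, because full follow-up leaves little room for screening tests.

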This study is a simple randomized clinical trial, its **objective** is to evaluate the effect of an aerobic physical exercise program on the reduction of triglycerides, blood pressure, abdominal obesity, altered glucose levels, and the increase in HDL in college-level students at the University of Colima, due to the high prevalence of obesity, a sedentary lifestyle, and physical inactivity in Mexican population, all of which contribute to a high risk for the development of metabolic disorders and cardiovascular diseases. **Methods and Materials:** A simple randomized clinical trial will be conducted with a **sample** of 48 voluntary students from the University of Colima, divided into two groups of 24 people. **Instruments:** IPA-Q questionnaire (*Annex 6*), waist circumference (*Annex 7*), blood pressure (*Annex 8*), blood extraction by a venous puncture for HDL, triglycerides, and blood glucose (*Annex 9*), Queen's College Step Test (*Annex 10*). **Procedure:** Once all the information from the tests is collected and processed, inclusion criteria (*table 2*) will be taken into consideration to obtain the total sample. Simple randomization will be carried out through a bag of sealed envelopes that will contain the letter of the group to which the subject belongs. Each participant will draw an envelope, write their name on it and hand it to the supervisor. Afterwards, these envelopes will be opened and participants will be assigned to the groups following the simple blind criteria, according to the letter on the envelope. The Experimental Group will undergo an aerobic physical exercise (APE) program involving jogging, swimming, and static cycling, three times a week with a duration of 60 minutes per exercise session with a progressive intensity, which will start at 57%-63% of the maximum heart rate (HRmax) in the first 4 weeks of the study, and will increase to 64% -76% in the final four weeks, fulfilling the principle of progressive overload. The control group will perform aerobic physical exercise, which will be walking at 57% to 76% of HRmax. **Expected results:** This intervention will lead to favourable changes in the disorders experienced by the intervention population and, at the same time, confirm the effectiveness of the planned aerobic physical exercise in reducing these risks.

Keywords: Exercise, Obesity, HDL, Triglycerides, Hypertension.

1. Introduction

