	Means	Day of the week	Duration	First four weeks intensity	Last four weeks intensity
Cardiorespiratory endurance	Walk	Monday	60 min	57% - 76% of HR Frequency	57% - 76% of HR Frequency
Cardiorespiratory endurance	Walk	Wednesday	60 min	57% - 76% of HR Frequency	57% - 76% of HR Frequency
Cardiorespiratory endurance	Walk	Friday	60 min	57% - 76% of HR Frequency	57% - 76% of HR Frequency

Source: Based on reference (83)

Table 12. General physical exercise prescription for the Experimental group (B).

	Means	Day of the week	Duration	First four weeks intensity	Last four weeks intensity
Cardiorespiratory endurance	Jogging	Monday	60 min	57% - 63% of HR Frequency	64% - 76% of HR Frequency
Cardiorespiratory endurance	Swimming	Wednesday	60 min	57% - 63% of HR Frequency	64% - 76% of HR Frequency
Cardiorespiratory endurance	Static Bicycle	Friday	60 min	57% - 63% of HR Frequency	64% - 76% of HR Frequency

Source: Self-made based on references (72, 114, 115)

Note: This planning will be adjusted in volume after the first 4 weeks, considering the subject's adaptations in the second test session.

Annexe 12. Borg Scale

Table 13. Modified Borg Scale

Modified Borg Scale	
0	Total rest
1	Very low effort
2	Soft
3	Moderated effort
4	A bit hard
5	Hard
6	Hard
7	Very hard
8	Very hard
9	Very hard
10	Maximal effort

Source: Self-made based on reference (116)

Annexe 13. Aerobic or Cardiorespiratory Fitness. Classification Scale. Estimated Maximum Oxygen Consumption (ml • kg-1 • min-1).

Aerobic or Cardiorespiratory Fitness. Classification Scale. Estimated Maximum Oxygen Consumption (ml • kg-1 • min-1).

Classification	Age groups (years)					
	13 - 19	20 - 29	30 - 39	40 - 49	50 - 59	Sobre 60
Men						
Very Poor	< 35.0	< 33.0	< 31.5	< 30.2	< 26.1	< 20.5
Poor	35.0-38.3	33.0-36.4	31.5-35.4	30.2-33.5	26.1-30.9	20.5-26.0
Average	38.4-45.1	36.5-42.2	35.5-40.9	33.6-38.9	31.0-35.7	26.1-32.2
Good	45.2-50.9	42.5-46.4	41.0-44.9	39.0-43.7	35.8-40.9	32.2-36.4
Excellent	51.0-55.9	46.5-52.4	45.0-49.4	43.8-48.0	41.0-45.3	36.5-44.2
Superior	> 56.0	> 52.5	> 49.5	> 48.1	> 45.4	> 44.3
Women						
Very Poor	< 25.0	< 23.6	< 22.8	< 21.0	< 20.2	< 17.5
Poor	25.0-30.9	23.6-28.9	22.8-26.9	21.0-24.4	20.2-22.7	17.5-20.1
Average	31.0-34.9	29.0-32.9	27.0-31.4	24.5-28.9	22.8-26.9	20.2-24.4
Good	35.0-38.9	33.0-36.9	31.5-35.6	29.0-32.8	27.0-31.4	24.5-30.2
Excellent	39.0-41.9	37.0-40.9	35.7-40.1	32.9-36.9	31.5-35.7	30.3-31.4
Superior	> 42.0	> 41.0	> 40.1	> 37.0	> 35.8	> 31.5

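### The elimination threshold in Table 4 contradicts itself: 19 of 24 sessions is 79.2%, below the stated 80% minimum, and the rule mixes a session count with program time that has no settled length in either arm.

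*Combined protocol and SAP*

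**What the plan says.** The elimination column of Table 4 (section 6.3) removes "Subjects failing to meet a minimum of 80% (19 out of 24 sessions) of the stipulated physical conditioning program time". That one phrase gives a percentage, a session count and a time basis. Nothing else in the document says how adherence is computed, how a partly attended session counts, or which of the three governs.

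Session length is described as follows.

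- **Experimental arm.** Section 9 has sessions "lasting 40 to 60 minutes, three times per week (Monday, Wednesday, and Friday) for eight weeks". The English abstract has "three times a week with a duration of 60 minutes per exercise session", and Annexe 11, Table 12 has 60 minutes on every line, for example "Jogging Monday 60 min".
- **Control arm.** Section 9 has "walking for 30 minutes at an intensity of 57% to 76% of the maximum heart rate, three times per week". Annexe 11, Table 11 has 60 minutes of walking on each of the three days.
- **Later change.** The note under Table 12 adds: "This planning will be adjusted in volume after the first 4 weeks".

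**The concern.** A minimum percentage and the count beside it should classify every participant the same way. Here they do not at one attendance value, 19 sessions, which is the limit the rule itself names. Counting sessions and counting time are also different measurements unless every session has the same length and is attended in full.

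The rule acts after randomisation, in groups of 24. Section 6.2 moves from 20 to 24 per group, a margin of four. Section 3 names poor adherence as a weakness of the study, so attendance near the limit is foreseeable. Section 11 names no analysis set, so the text does not say whether an eliminated participant's data are still analysed. Only participants are described as blinded, and the principal investigator supervises the experimental sessions. A rule with more than one reading would therefore be applied by people who know allocation and attendance. How eliminated participants should be analysed is a separate question and is not argued here.

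**Working it through.** **Inputs.** Frequency and duration: 3 sessions per week for 8 weeks (section 9). Threshold: 80%, given as 19 of 24 (Table 4). Session lengths: 40 to 60 or 60 minutes, experimental arm; 30 or 60 minutes, control arm (section 9, abstract, Annexe 11). Sample: 48 (abstract and section 9).

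**Step 1: the plan's own figures.** 3 × 8 = 24 sessions, which reproduces. 0.80 × 24 = 19.2. The stated 19 is obtained by rounding 19.2 down or to the nearest whole number. A minimum has to be rounded up, which gives 20.

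| Sessions attended | Share of 24 | Meets the count of 19? | Meets 80%? |
|---|---|---|---|
| 18 | 75.0% | no | no |
| 19 | 79.2% | yes | no |
| 20 | 83.3% | yes | yes |

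The two versions differ only at 19, by 80 − 79.17 = 0.83 percentage points.

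**Step 2: does the time wording rescue the count?** With a fixed 60 minutes, stipulated time is 24 × 60 = 1440 minutes and 80% of it is 1152. Nineteen full sessions give 19 × 60 = 1140 minutes, or 79.2%. With any fixed length the ratio is the same 19/24, so the mismatch remains.

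**Step 3: what if length is not fixed?** Suppose, as an assumption within the range in section 9, that a participant is prescribed 40 minutes in weeks 1–4 and 60 minutes in weeks 5–8. Stipulated time is 12 × 40 + 12 × 60 = 1200 minutes. With 19 sessions attended:

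- the five missed are 40-minute sessions: (1200 − 200)/1200 = 83.3%;
- the five missed are 60-minute sessions: (1200 − 300)/1200 = 75.0%.

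The same count falls on either side of 80% of time, so the two units are not interchangeable.

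**Step 4: how many participants might sit at 19?** The documents give no attendance figure. As an illustration, let attendance be binomial with n = 24 and a common, independent per-session probability p. Then P(X = 19) = C(24,19) p^19 (1 − p)^5.

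| p (assumed) | P(exactly 19) | Expected of 48 |
|---|---|---|
| 0.75 | 0.176 | 8.4 |
| 0.80 | 0.196 | 9.4 |
| 0.85 | 0.147 | 7.1 |
| 0.90 | 0.057 | 2.7 |
| 0.95 | 0.005 | 0.2 |

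The probability peaks at p = 19/24 = 0.79, so about 9 of 48 is close to the most this model can give. At high attendance the number is near zero.

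**The case against.** The strongest reply is that 19 is simply 19.2 rounded, that the bracket is the working form of the rule, and that a whole-number count fixed in advance leaves nobody's status in doubt. The origin is probably just that. But the sentence calls 80% a minimum and does not say that the count prevails, so the contradiction at 19 sessions stands. It is confined to that single value.

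Three stronger inferences are tempting, and the documents do not support them.

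- *A participant with perfect attendance at 40 minutes would be eliminated on time.* The figure behind this, 24 × 40 / 1440 = 66.7%, takes the numerator from section 9 and the denominator from Table 12. Section 9 also says each experimental prescription is individual. Someone prescribed 40 minutes who attends all 24 sessions has done 960 of 960 minutes, or 100%. Under Table 12, 40-minute sessions are not prescribed at all. What survives is that the denominator is unsettled.
- *A time reading falls mainly on the experimental arm.* The control arm has its own conflict. The same mixed calculation gives 24 × 30 / 1440 = 50%, lower than 66.7%. No direction of imbalance can be claimed.
- *The reading will be chosen after attendance is known.* The text leaves that possible; nothing in it shows that it is intended.

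It is also fair to say that the binomial model ignores withdrawals, other eliminations and differences between participants. Its range is only an illustration.

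**Conclusion.** The point holds in two limited parts. First, the percentage and the count in Table 4 classify a participant with exactly 19 sessions in opposite ways; this is plain arithmetic and needs no assumption. Second, the sentence joins a session count to a time measure, and the session lengths needed for the time measure conflict within each arm, so a time reading cannot be applied consistently in either arm.

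The size is minor. One attendance value is affected by the first part, and the number of people at that value is unknown: roughly 0 to 9 of 48 under the assumed range of 0.75 to 0.95. The second part cannot be quantified from the documents. It still deserves correction, because the threshold decides who is removed after randomisation and the repair is cheap.

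**What to change.** Before enrolment, rewrite the one line in Table 4 so that percentage, count and unit agree. Use sessions attended as the only unit, apply the same rule in both arms, and state one consistent pair: 20 of 24 (83%) or 19 of 24 (79%). Either removes the contradiction, and the choice is the sponsor's. If time is kept as the unit, the session lengths in the abstract, section 9 and Annexe 11 (Tables 11 and 12, with the note on volume) must first be reconciled, and the line must say what counts as stipulated time. This review takes no position on which session length is right.

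The cost is one line of text. There are two downsides. With sessions as the unit, a session left early counts as attended. With the 20-session version, participants with exactly 19 sessions are classed as non-compliant.
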